1. PURPOSE OF THE STUDY

a. Brief Summary

Minimizing bleeding during endoscopic sinus surgery is important for optimal patient outcome. Since there is a great variation in the structure of the sinuses among the population, without a clear surgical field, there may be inadvertent injury to the surrounding structures or an incomplete opening of sinuses. We hope to learn the best method for controlling bleeding i the field of view to help optimize the surgical outcome.

b. Objectives

We hope to learn the preparation for the best field of view with minimal bleeding that may interfere with the visualization for endoscopic sinus surgery. Studies in the past commonly looked at the estimated blood loss which may not reflect the actual surgical field. We would like to assess the actual surgical field to help determine the best possible technique to optimize endoscopic sinus surgery.

c. Rationale for Research in Humans

Human subjects must be used because the purpose of the study is to study the method which provides the best field of view for endoscopic sinus surgery in human.

2. STUDY PROCEDURES

a. Procedures

We will first perform chart review to screen for patients who were scheduled for endoscopic sinus surgery for rhinosinusitis that meet both our inclusion and exclusion criteria. We will check the date of the patient's next visit to meet them and explain the study protocol and ask for their consent. If they consent to the study, on the day which they have the surgery we will follow the protocol, giving topical adrenaline on both side and infiltrating lateral nasal wall with the medication according to the study (patient will receive 1% xylocaine with adrenaline (1:100,000) on one side and saline on the contralateral side, they will be randomized to which side receive which solution for infiltration). The Estimated blood loss on each side and the duration of the surgery on each side will also be recorded. The Video of the surgery will be evaluated by 2 different otolaryngologists to give grading score for surgical field of view using Wormald Surgical

Field Grading Scale. Patients will have regular post operative follow up as for endoscopic sinus surgery. At the patient's first follow up at 1 week after the surgery, the patient will be asked to fill out a questionnaire about the postoperative bloody discharge they experienced.

b. Procedure Risks

Any medications may lead to inadvertent effects, however the use of infiltration of xylocaine with adrenaline is widely accepted and has originally been used in preparation for endoscopic sinus surgery and also for variety of surgical procedures both under general and local anesthetic. With correct route and dosage given, infiltration performed by specialist under a well-controlled circumstance as under general anesthesia where patient's vital signs are closely monitored we believe that it is safe to perform the procedure. Topical adrenaline has recently gained popularity among a number of surgeons world wide in the use for endoscopic sinus surgery and has known to be safe and potent with great result in bleeding control.

c. Use of Deception in the Study

Deception will not be used to enroll the patient. We will not perform the procedure without the patient's consent.

d. Use of Audio and Video Recordings

Video recording will be performed in the study (our department usually has all the surgeries recorded as a routine procedure). This will be reviewed by 2 otolaryngologists at Stanford's university (attendings or rhinology fellows). The otolaryngologist reviewing and grading the video will be blinded to which side of the sinus surgery was performed under only topical adrenaline or with the combination of both topical and infiltration of adrenaline. The video given will be labeled by the number and not by name of the patient and the video will be secure with passcode lock external hard disk.

e. Alternative Procedures or Courses of Treatment

Many different methods and many different agents have been used to help reduce bleeding in endoscopic sinus surgery. Currently, adrenaline has become the consensus as the best agent used for this purpose; however, there is no one consensus method of delivery, each center practices according to their experience for the best of the patients. At our center, half of the team use only topical adrenaline before the surgery and the other half combine infiltration of xylocaine with adrenaline with topical adrenaline. Therefore, the alternative at our center depends on the surgeon's experience between topical adrenaline only and topical adrenaline combine with infiltration. In this study the participant instead of one or the other will get a combination of pure topical on one side and combine topical with infiltration on the other side of the nasal cavity. Using both topical and infiltration of adrenaline may result in less bleeding and better field of view, however infiltration of adrenaline may have potential side effect e.g. cardiovascular and central nervous system side effects. However, xylocaine with adrenaline is a widely used anesthesia and administering at appropriate dosage and route under an extremely well controlled environment as being under general anesthesia in the operating room where all patient's vital signs are monitored shouldn't be risky. Now that topical adrenaline is more

widely used than before we want to examine the benefit of additional infiltration of adrenaline to the surgical field of view to determine the best optimal practice for endoscopic sinus surgery.

f. Will it be possible to continue the more (most) appropriate therapy for the participant(s) after the conclusion of the study?

After the study, the participants will be able to use any therapy that is appropriate for them.

g. Study Endpoint(s)

The study will end after the required number of participant has been enrolled. Since both method is the standard we currently perform at the department we do not expect any harmful results to the participants.

3. BACKGROUND

a. Past Experimental and/or Clinical Findings

In the past there have been studies which tried to address the best methods to help optimize the surgical field. However, none has actually compared the injection of adrenaline to the control using a proper endoscopic grading score (which is a more accurate way of assessing visual field in comparison to using the estimated blood loss). Since estimated blood loss may give just a crude estimate of the surgical field, we suspect that it may be the reason why the previous studies couldn't demonstrate the significant of infiltration of adrenaline to the surgical field of view in endoscopic sinus surgery.

b. Findings from Past Animal Experiments

Animal studies were not identified in our literature review.

4. RADIOISOTOPES OR RADIATION MACHINES

N/A

5. DEVICES USED IN THE STUDY

N/A

6. DRUGS, BIOLOGICS, REAGENTS, OR CHEMICALS USED IN THE STUDY

a. Investigational Drugs, Biologics, Reagents, or Chemicals

N/A

b. Commercial Drugs, Biologics, Reagents, or Chemicals

Commercial Product 1	
Name:	1%Xylocaine with adrenaline
Dosage:	1%
Administration Route	Intranasal infiltration
New and different use? (Y/N)	No

7. DISINFECTION PROCEDURES FOR MEDICAL EQUIPMENT USED ON BOTH HUMANS AND ANIMALS

N/A

8. PARTICIPANT POPULATION

a. Planned Enrollment

- (i) 40 participants to be enrolled at Stanford
- (ii) total of 40 participants overall (the study will only be performed at Stanford)
- (iii) the participants will be the patients from the rhinology clinics who have sinusitis that have failed medical treatment and were scheduled for endoscopic sinus surgery

b. Age, Gender, and Ethnic Background

Age range 18-75 years old Both males and females All ethnic backgrounds

c. Vulnerable Populations

Potentially vulnerable subjects (including children, pregnant women, economically and educationally disadvantaged, decisionally impaired, homeless people, employees and students) will not be enrolled in the study.

d. Rationale for Exclusion of Certain Populations

Women and minorities are included, however children are not included since endoscopic sinus surgery is not widely perform in children.

e. Stanford Populations

The study will not involve participants who are laboratory personnel, employees and students.

f. Healthy Volunteers

We do not take healthy volunteers for the study since they would have no indications for the surgery.

g. Recruitment Details

We will identify the participants for recruitment by chart review prior to their preoperative visit. No flyers or other advertisement will be used in the study.

h. Eligibility Criteria

i. Inclusion Criteria

1. Patients between the age of 18-75 years old who were diagnosed with recurrent acute or chronic rhinosinusitis that are recalcitrant to medical treatment and were scheduled for endoscopic sinus surgery

ii. Exclusion Criteria

- 1. Patients who have asymmetrical disease on the two sides (Lund Mackay score difference of 2 or more)
- 2. Patients who have endoscopic sinus surgery for treatment of tumor or disease other than sinusitis
- 3. Patients with nasal polyps
- 4. Patients with underlying uncontrolled hypertension
- 5. Patients with bleeding disorder or are unable to discontinue antiplatelet or anticoagulant before the surgery
- 6. Patients who are allergic to adrenaline or to xylocaine
- 7. Patients who are not consent to the procedure

i. Screening Procedures

Screening will be done by chart review. Personal health information, e.g., patient's history, symptoms, prior treatment, endoscopic and computer tomography of paranasal sinus findings may be reviewed to see if the patient may fit the inclusion criteria. If the patient meets the criteria then on the patient's preoperative visit we will explain the study and discuss enrollment. No additional laboratory test apart from their routine preoperative test will be required.

j. Participation in Multiple Protocols

Participants will not be enrolled in more than one study. The consent form will include the question to whether they are enrolled in other studies or not and the protocol director taking the consent will ask the question before explaining the research protocol.

k. Payments to Participants

There is no payment for enrolling in the study.

I. Costs to Participants

There will be no charge to the participant.

m. Planned Duration of the Study

The probable duration of the entire study is 10 months. The estimated total time per participant is approximately 2 weeks, starting on the day for screening and asking for consent from the participant which will usually be on the preoperative visit which is usually about a week before the surgery. Conducting the actual study will happen during the time the participant is in the operating room, then at the first postoperative visit which usually take place 1 week after the surgery, a short questionnaire will be given for the participant to fill out.

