## 1. STATISTICAL METHODS

A prestudy power analysis was completed with Monte Carlo simulations to estimate the necessary sample size. A sample size of 38 patients in total would give the power of 82% with type I error of 0.05 to detect the difference in Wormald scale between the 2 groups. Patient-level demographics and baseline clinical factors were summarized with mean (standard deviation) for continuous variables and with n (%) for categorical variables. The comparisons of clinical variables (all continuous) between both sides of the nose were performed using paired t test. To estimate the effect of 1% lidocaine with 1:100,000 epinephrine, we constructed a mixed effect models with random slope by accounting for within-subject correlation. All the models were adjusted for age, gender, preoperative Lund-Mackay score, preoperative Lund-Kennedy score, and medication use. Surgery time was found to be right-skewed; therefore, it was log-transformed in the model, and the regression coefficient was exponentiated to represent the percentage difference. We performed reliability testing for the Wormald scale graded by 2 graders, by calculating the intraclass correlation coefficient (ICC) as well as its 95% confidence interval (CI).

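### Planned extent of surgery on each side is neither controlled at entry nor included in the models, which adds noise to the blood-loss and surgery-time comparisons

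*Protocol*

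**What the plan says.** **Eligibility.** The single inclusion criterion (Protocol, 8h(i)) requires rhinosinusitis "recalcitrant to medical treatment and were scheduled for endoscopic sinus surgery". The only criterion on side-to-side comparability is the first exclusion in 8h(ii): "Patients who have asymmetrical disease on the two sides (Lund Mackay score difference of 2 or more". That criterion is about disease score. Nothing in 8h, or in the chart-review screening of 8i, mentions which sinuses will be opened or how many on each side.

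**Design and outcomes.** Each patient has active infiltration on one side and saline on the other, and "they will be randomized to which side receive which solution for infiltration" (Protocol, 2a). The same section adds: "The Estimated blood loss on each side and the duration of the surgery on each side will also be recorded".

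**Analysis.** In the SAP, comparisons "between both sides of the nose were performed using paired t test". The treatment effect is then estimated with mixed models "adjusted for age, gender, preoperative Lund-Mackay score, preoperative Lund-Kennedy score, and medication use", with surgery time log-transformed.

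**Size.** The SAP states: "A sample size of 38 patients in total would give the power of 82% with type I error of 0.05", for the Wormald scale. Protocol 8a plans "40 participants to be enrolled at Stanford".

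**The concern.** In a within-patient comparison the two sides should differ only in the infiltration, apart from random variation. The plan recognises this for disease burden by excluding marked Lund-Mackay asymmetry. It does not do so for the operation itself, whose duration and blood loss are measured separately on each side. If more sinuses are opened on one side, that side can be expected to take longer and bleed more, whatever was injected.

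What is at stake is the precision of two outcomes: blood loss and surgery time. The Wormald grade describes the quality of the field and is less directly tied to how many sinuses are opened.

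**Working it through.** **1. The plan's own figure.** The 82% cannot be reproduced, because the SAP gives no effect size, standard deviation, within-patient correlation or sidedness. It can be back-solved. For a paired t test, T follows a noncentral t distribution with n − 1 degrees of freedom and noncentrality dz × √n, where dz is the mean paired difference divided by its standard deviation. Setting n = 38, alpha = 0.05 two-sided (assumed) and power 0.82 gives dz = 0.479, with noncentrality 0.479 × √38 = 2.95. If the test were one-sided, dz would be 0.423. This is an implied effect for the Wormald scale only.

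**2. Can any existing covariate absorb unequal extent?**

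| SAP covariate | Can it explain a side-to-side difference in extent? |
|---|---|
| Age, gender | No; identical on both sides |
| Medication use | No, if it means the patient's own medication |
| Lund-Mackay score | Only if entered per side, which is not stated; even then it scores disease, and eligible sides differ by at most 1 |
| Lund-Kennedy score | Only if entered per side, which is not stated; not a measure of extent of surgery |

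**3. What unequal extent does.** For patient i, let k be the planned number of sinuses on the more extensive side minus the number on the other. Let s = +1 if the active infiltration falls on the more extensive side and −1 otherwise. With β the effect of one extra sinus on the outcome, the paired difference is

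d = τ + β·s·k + ε.

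If the side is randomised with equal probability and the plan is fixed before allocation is known, s is independent of k and E(s) = 0. Therefore:

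- E(d) = τ, so there is no bias.
- Var(d) = σ² + β²·E(k²), so there is added variance.
- The standard error is multiplied by √(1 + r), with r = β²·E(k²)/σ².

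The documents give none of β, E(k²) or σ for blood loss or log time, so r is unknown. To show only what the formula means, assumed values of r = 0.1, 0.2, 0.3 and 0.5 give multipliers √1.1 = 1.05, √1.2 = 1.10, √1.3 = 1.14 and √1.5 = 1.22. These are not estimates for this trial.

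**4. One-sided patients.** A patient operated on one side gives no pair. Starting from the 40 planned and using dz = 0.479:

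| One-sided patients | Pairs left | dz × √n | Power (Wormald) |
|---|---|---|---|
| 0 | 40 | 3.03 | 84.0% |
| 2 | 38 | 2.95 | 82.0% |
| 4 | 36 | 2.87 | 79.8% |

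The two patients planned above 38 absorb the first two losses.

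**The case against.** The strongest reply is that the plan already presupposes two operated sides. Protocol 2a sets active solution against saline on the opposite side and records duration for each. Sections 2d and 2e describe blinded grading of the sides and one preparation per side. A one-sided case could not complete these procedures. This stands. A reader might infer from 8h alone that one-sided patients will enter and drain the trial of power, but the documents do not support that. The missing word is a matter of clarity, and the margin of 40 over 38 covers a small number. The mixed models could also use a single-side observation, although the paired t test could not.

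A second reply is that exclusion 1 already limits asymmetry. It does make very unequal surgery less likely, but it constrains a CT disease score and leaves the operation free. This reply stands in part.

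A third is that the Lund-Mackay adjustment covers the matter. Step 2 of the working shows that it can do so only in part, and only if it is entered per side.

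It is also tempting to attach a power loss to unequal extent by inflating the variance around the implied effect of 0.479. That is not supported. The effect belongs to the Wormald scale, no power was planned for blood loss or time, and the frequency and size of unequal extent would have to be invented.

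**Conclusion.** The point holds as a modest loss of precision in two comparisons, blood loss and surgery time per side. Extent of surgery is neither controlled at entry nor represented in the models. The size of the loss cannot be derived from the documents.

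A reader might infer that unequal extent biases the treatment comparison. It does not, provided that the side is allocated with equal probability and the surgical plan is fixed before allocation is known. In a trial of about 40, chance imbalance remains possible, but that is part of the same added variance. Nor do the documents show any fall in the stated 82% power from unequal extent.

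The bilateral-surgery wording is a clarification. Its effect on power is nil against the SAP target for up to two one-sided patients and about 2 points (82.0% to 79.8%) for four. This assumes a two-sided paired t test and the back-solved effect.

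**What to change.** 1. **Record** the planned number of sinuses to be opened on each side before randomisation. Use the planned number, not the number finally opened. Protocol 1a itself says that a poor field may leave sinuses incompletely opened, so the final number could be affected by the treatment and is not a safe covariate.
2. **Model** it: add that number as a side-level covariate in the SAP mixed models for blood loss and log surgery time. The paired t tests for these outcomes stay unadjusted and should be read alongside the adjusted estimates.
3. **Clarify** in 8h(i) that the scheduled surgery is bilateral, in line with Protocol 2a, 2d and 2e.

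The cost is one recorded field per side, one model degree of freedom and one word in the eligibility text. A criterion requiring the same sinuses on both sides is not needed: it would narrow the population by an unknown amount, and the covariate deals with the same source of noise without excluding anyone.

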9. RISKS

a. Potential Risks

i. Investigational devices

The study doesn't involve an investigational device.

ii. Investigational drugs

The study doesn't involve an investigational drug.

iii. Commercially available drugs, biologics, reagents or chemicals

Irritation to infiltration site, persistent paresthesia, central nervous system excitatory or depressant effect which may cause headache, nausea, ringing in the ear, confusion, cardiovascular effect such as bradycardia, hypotension and cardiovascular collapse or tachycardia, palpitations and hypertension, hypersensitivity reaction.

Correct route and dosage of the medication is important to avoid the adverse effects, the medication will be infiltrated by specialist the study.

iv. Procedures

The procedure is intranasal infiltration of 1% xylocaine with adrenaline which is a routine procedure in endoscopic sinus surgery.

v. Radioisotopes/radiation-producing machines

There will be no use of radioisotopes/radiation-producing machine for the study.

vi. Physical well-being

We do not anticipate that participants in this study will be placed at risk in terms of physical well-being.

vii. Psychological well-being

We do not anticipate that participants in this study will be placed at risk in terms of psychological well-being.

viii. Economic well-being

We do not anticipate that participants in this study will be placed at risk in terms of economic well-being.

ix. Social well-being

We do not anticipate that participants in this study will be placed at risk in social well-being.

x. Overall evaluation of risk

Low risk

b. International Research Risk Procedures

N/A

c. Procedures to Minimize Risk

Overall potential risk to the patient should be very low. The patient will get the infiltration right before the surgery after general anesthesia where the vital signs will be closely monitored in the intra operative setting by anesthesiologist. Also any intranasal bleeding from the surgery is easily controlled in the operating room under endoscopic view with medications and equipment set up ready for the surgery.

d. Study Conclusion

The participants will only be given one dose of the infiltration throughout the study. If any adverse effects were to happen, the participant will be terminated from the study and will be closely taken care of. As the infiltration will take place in the operating room after the patient is under general anesthesia, where the patient will be fully monitored, any adverse effects would be easily detected at a very early stage and best appropriate treatment will be given.

e. Data Safety Monitoring Plan

i. Data and/or events subject to review

Monitoring will include bleeding intraoperatively and postoperatively, the visual field grading scale score, patient's vital sign intraoperatively, the overall blood loss on each side, the operative time on each side.

ii. Person(s) responsible for Data and Safety Monitoring

The protocol director, co-protocol director and academic sponsor will be responsible for data and safety monitoring of the study.

iii. Frequency of DSMB meetings

The protocol director will meet with the other researchers conducting the study on a weekly basis (every Monday evening) to review the protocol.

iv. Specific triggers or stopping rules

Any major complications secondary to the study will terminate the study. However, this is very unlikely since intranasal infiltration of xylocaine with adrenaline is a routine procedure perform for endoscopic sinus surgery and infiltration at correct dosage and by specialist under well controlled environment shouldn't result in any major complications.

v. DSMB Reporting

The IRB will be informed if any abnormal outcomes were to occur.

vi. Will the Protocol Director be the only monitoring entity? (Y/N)

Yes

vii. Will a board, committee, or safety monitor be responsible for study monitoring? (Y/N)

No

f. Risks to Special Populations

N/A

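### Protocol 9d ends participation for any adverse effect after the only dose has been given, and the plan secures neither those participants' data nor a count of their events

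*Protocol*

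**What the plan says.** Protocol 9d (Study Conclusion) states: "If any adverse effects were to happen, the participant will be terminated from the study and will be closely taken care of". No severity, relatedness or timing condition is attached. The same section says: "The participants will only be given one dose of the infiltration throughout the study". Protocol 9c places that dose before the operation: "The patient will get the infiltration right before the surgery after general anesthesia". Protocol 9d also expects that "any adverse effects would be easily detected at a very early stage".

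The effects listed in Protocol 9a.iii run from headache and nausea to "cardiovascular effect such as bradycardia, hypotension and cardiovascular collapse or tachycardia, palpitations and hypertension, hypersensitivity reaction". Protocol 9c nevertheless judges that "Overall potential risk to the patient should be very low".

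A separate rule in Protocol 9e.iv acts on the whole trial: "Any major complications secondary to the study will terminate the study". Protocol 9e.i lists what is monitored: bleeding, field score, intraoperative vital signs, and blood loss and operating time by side. Protocol 9e.v adds: "The IRB will be informed if any abnormal outcomes were to occur".

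SAP section 1 covers the power simulation, baseline summaries, paired t tests, adjusted mixed models and grader reliability. It names no analysis set, no handling of terminated participants or missing data, and no adverse-event summary. Neither document says whether a terminated participant is replaced.

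**The concern.** Withdrawing a patient from study treatment is sensible when more treatment is to come. Here the exposure under test is complete before the first outcome is measured, so ending participation cannot take the dose back. It can end data collection in the patients who reacted.

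Two things are at stake. The first is data: at least the one-week questionnaire and, for a reaction under anaesthesia, possibly the field grade, blood loss and time on both sides. The second is harm reporting. Protocol 2e frames the question as the benefit of adding infiltration, set against possible cardiovascular and central nervous system effects. A rule that removes reactors, with no planned event count, puts the second half of that comparison at risk. Because no analysis set is named, whether to keep such a patient could also be decided after the grades are known.

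**Working it through.** **Step 1. Which data the rule can reach.** The order of events (Protocol 2a and 9c) is infiltration under anaesthesia, then surgery with video, blood loss and time by side, then the questionnaire at one week.

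| Event | Rule | Data at risk |
|---|---|---|
| Non-major effect seen under anaesthesia (blood pressure, heart rate, hypersensitivity) | 9d | Field grade, blood loss, time, questionnaire |
| Symptom after waking (headache, nausea) | 9d | Mainly the questionnaire; the video already exists |
| Major complication | 9e.iv stops the study | Handling of that patient's data not stated |

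**Step 2. The plan's own power figure.** SAP section 1 gives 82% power at 38 patients with type I error 0.05, by simulation. It gives no effect size, standard deviation, within-patient correlation or sidedness, so 82% cannot be reproduced. As an approximation, take a two-sided paired t test:

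power(n) = P(|T| > t at 0.975 with n − 1 df), where T is noncentral t with n − 1 df and noncentrality d√n.

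Setting power(38) = 0.82 gives d = 0.479 SD of the side difference. At n = 36 the noncentrality is 0.479 × 6 = 2.874.

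| Complete pairs | 40 | 38 | 36 | 34 | 32 |
|---|---|---|---|---|---|
| Power | 84.0% | 82.0% | 79.8% | 77.4% | 74.7% |

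Protocol 8a plans 40 participants, so the margin over 38 is 2. Losing 4 pairs takes power from 84.0% to 79.8%, which is 2.2 points below the stated 82%.

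**Step 3. How often the rule would be triggered.** The documents give no adverse-effect rate, so 2% to 10% is assumed. With X ~ Binomial(40, p), P(X ≥ 1) = 1 − (1 − p)^40.

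| Assumed rate p | Expected terminations, 40p | P(at least 1) | P(3 or more) |
|---|---|---|---|
| 2% | 0.8 | 55% | 5% |
| 5% | 2 | 87% | 32% |
| 10% | 4 | 99% | 78% |

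These rates cover every adverse effect. Only the first row of the Step 1 table threatens a whole pair, so pairs would be lost less often than this.

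**Step 4. Harm reporting in the worst case.** Suppose terminated patients left both numerator and denominator. Exact (Clopper-Pearson) 95% limits:

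| True count | 95% CI | Would appear as | Upper limit, 1 − 0.025^(1/n) |
|---|---|---|---|
| 1/40 (2.5%) | 0.1–13.2% | 0/39 | 9.0% |
| 2/40 (5%) | 0.6–16.9% | 0/38 | 9.3% |
| 4/40 (10%) | 2.8–23.7% | 0/36 | 9.7% |

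**Step 5. Bias in the side difference.** The analysed quantity is one side minus the other within a patient. Dropping a patient removes both sides, so the arms stay balanced. A systemic change in pressure or heart rate reaches both sides and tends to cancel in the difference. Selection would matter only if reacting went together with the size of the local benefit, and nothing in the documents indicates that.

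**The case against.** The strongest reply is that 9d is participant-protection wording in the risk section, not a data rule. It does not say that recorded data are discarded, and the SAP excludes nobody. Harms are watched: vital signs and bleeding are reviewed, the team meets weekly, and the IRB is told of abnormal outcomes. The protocol expects few events, and even 4 lost pairs cost little power.

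Much of this stands. A reader might infer that terminated patients' grades will be deleted and their events hidden; no text says so, and Step 4 is a worst case. A reader might also infer that termination can do nothing except lose data. That goes too far, because it may free the surgeon from the saline assignment or other study constraints so that care follows clinical need. The documents also do not say whether both sides are infiltrated before either is operated on.

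What the reply does not meet is the rule as written. Ending participation ends the one-week questionnaire on any ordinary reading, and safety oversight is not a commitment to tabulate events in the results. Clinical freedom can be given without ending follow-up.

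**Conclusion.** The point holds and is minor. Protocol 9d removes from the study, with no severity threshold, patients who have already had the only dose. The plan does not say that their outcomes are kept or their events counted. The cost is avoidable loss of data and of harm reporting. In power terms it is about 79.8% at 36 pairs, provided that 82% at 38 is right and a two-sided paired t test approximates the SAP's simulation. How often the rule would bite depends on an adverse-effect rate that the documents do not give.

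A reader might infer that dropping reactors materially biases the estimated benefit or inflates the type I error. The documents do not support that. It would need recorded data to be discarded and reactors to differ clearly from other patients in local benefit, while the reactions most likely to endanger the field grade act on both sides.

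**What to change.** **Protocol 9d.** Replace the termination sentence with: 'A participant with an adverse effect is treated as clinically needed, including release from any remaining study procedure, and stays in follow-up. The video is graded, blood loss and time on each side are recorded, and the questionnaire is taken, unless consent is withdrawn or surgery is abandoned.' Leave the 9e.iv stopping rule unchanged.

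**SAP section 1.** Add: 'The analysis set is all randomised participants who were infiltrated and had surgery. Adverse events are reported per patient as n/N with an exact 95% confidence interval, N being all infiltrated participants.' Local events can be given by side. Systemic events cannot be compared by side, because each patient receives both solutions.

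**Cost.** The new text is a few sentences, but it alters a safety provision and should be reviewed as one. Where surgery goes ahead, no new visit, procedure or staff is needed: Protocol 2d says that operations are usually recorded anyway, and blood loss and time are already collected by side.

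**Downside.** An operation disturbed by a reaction, or by its treatment between the two sides, may add noise or some distortion to the side difference. A sensitivity analysis without such patients is optional, and with so few of them it would show little.
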